6.3.3.2 Data to Be Collected from Withdrawn Subjects

All data from evaluations and treatments performed prior to the withdrawal should be documented on the CRFs. Source documents and angiograms that pre-date the withdrawal should be submitted

as required by the clinical investigation plan. No data that post-dates the withdrawal will be collected.

6.3.3.3 Follow-up for Withdrawn Subjects

Once a subject has withdrawn from the trial, no further follow-up contact will be performed. However, vital status will be obtained from public records.

6.3.4 Point of Enrollment

Given the relatively low incidence of PCI to long lesion (8.4% in the ADAPT-DES trial), and the fact that the EluNIR 38 mm stent is approved and marketed in Israel, patients will be consented after PCI. Once a patient has met all general and angiographic eligibility criteria, a 38 mm long EluNIR stent been passed beyond the guiding catheter, and the patient has signed an informed consent (post-procedure), the patient will be enrolled into the trial. If the study stent is not advanced into the guiding catheter, the subject will not be consented and not be enrolled.

In order to minimize selection bias, all eligible patients (meeting I/E criteria and in whom a 38 mm long EluNIR stent was advanced beyond the guiding catheter) will be approached for participation in the study, regardless of final procedure outcome.

The sites will maintain a screening log of all 38 mm EluNIR stents advanced beyond the guiding catheter and document eligibility and patient consent versus refusal to participate in the study.

The screening and enrollment process is displayed in [Figure 1](#).

[figure not shown]

Figure 1: Screening and Enrollment Flow Chart

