6.1.4 Methods and Timing for Assessing, Recording, and Analyzing Variables

Data collection commences after the subject has provided an informed consent. Data collection including subject demographic information, laboratory tests, and procedural data as well as follow-up visits or telephone contacts will be conducted by an Investigator or site coordinator who has been trained on the CIP and Case Report Forms (CRF).

Data required for analysis will be obtained as outlined in **Table 1**. After discharge from the hospital, each subject will be followed with an in-clinic follow-up visit at 30 days, and follow-up by phone at 6 months and 1 year post procedure.

Table 1: Schedule of Data Collection

TYPE OF DATA TO BE COLLECTED	Pre-Procedure ¹ (within 30 days)	Pre-Procedure ¹ (within 24 hours)	Baseline Procedure	Post-Procedure	30 days (± 7 days)	6 Months (± 30 days) by phone	1 year (-30 days / +14 days) by phone	Unscheduled visits
Patient Informed Consent				✓				
Patient Medical/Clinical History				✓ ¹				
Angina Status		✓ ¹		✓ ¹	✓	✓	✓	✓
General Eligibility Criteria			✓ ¹					
Angiographic Eligibility Criteria			✓ ¹					
Clinical Laboratory Tests:								
CBC, Creatinine, BUN	✓ ^{1,2}							
Lipid profile	✓ ^{1,2}							
CK, CK-MB or Troponin		✓ ¹⁻³		✓ ⁴				
12-Lead ECG		✓ ¹		✓				
Coronary Angiogram & PCI			✓ ¹					
Study Stent Information			✓ ¹					
Per Protocol DAPT Medications ⁵		✓ ¹	✓ ¹	✓	✓	✓	✓	✓
Concomitant Cardiac Medications ⁶		✓ ¹		✓	✓	✓	✓	✓
Adverse Events Monitoring			✓ ^{1,7}	✓	✓	✓	✓	✓

1. Data will be collected only after post-procedural informed consent has been obtained.
2. Should be collected at time of enrollment if not collected at baseline as part of routine SOC.
3. Within 24 hours pre-procedure if collected per site protocol. For subjects with ACS, it is recommended that enzyme levels be within 8 hours of the procedure or have already been shown to be decreasing. For STEMI patients enzyme levels should have peaked for either CK-MB or Troponin (I or T) or both.
4. If Troponin is elevated or CK-MB is elevated \geq upper limit of normal, serial measurements of CK and CK-MB (preferred) or Troponin (I or T) must be done until a decline is noted
5. Clopidogrel 75 mg daily or prasugrel 5 to 10 mg daily or ticagrelor (90 mg bid) must be given for a minimum of 6 months (12 months in ACS patients) as well as aspirin 75 to 100 mg daily to be taken indefinitely.

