6.1.6 Procedures for the Replacement of Subjects

Discontinued subjects will not be replaced. Patients who do not consent to be enrolled in the study will not count towards the sample size of approximately 50 subjects and will not be included in the FAS.

Patients who are consented but do not meet eligibility and are not in the FAS will be in the Safety Analysis Set which will also include all FAS patients. Safety Analysis Set patients will be followed until resolution of any adverse events related to study procedures.

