6.3.1 Inclusion Criteria for Subject Selection

All inclusion criteria must be present for the patient to be eligible for enrollment.

Note: the I/E criteria refer to the patient's baseline condition prior to PCI.

General Inclusion Criteria

1. Age ≥ 18 years.
2. Patient with an indication for PCI including angina (stable or unstable), silent ischemia (in absence of symptoms a visually estimated target lesion diameter stenosis of $\geq 70\%$, a positive non-invasive stress test, or FFR ≤ 0.80 must be present), NSTEMI, or recent STEMI. For STEMI the time of presentation to the first treating hospital, whether a transfer facility or the study hospital, must be >24 hours prior to enrollment and enzyme levels (CK-MB or Troponin) demonstrating that either or both enzyme levels have peaked.
3. An attempt (whether successful or not) was made to implant a 38 mm EluNIR stent (Stent was advanced beyond the guiding catheter).

4. Non-target vessel PCI are allowed prior to enrollment depending on the time interval as follows:

a. During Baseline Procedure:

PCI of non-target vessels performed during the baseline procedure itself immediately prior to enrollment if successful and uncomplicated defined as: <50% visually estimated residual diameter stenosis, TIMI Grade 3 flow, no dissection \geq NHLBI type C, no perforation, no persistent ST segment changes, no prolonged chest pain, no TIMI major or BARC type 3 bleeding.

b. Less than 24 hours prior to Baseline Procedure:

Not allowed (see exclusion criteria #2).

c. 24 hours-30 days prior to Baseline Procedure:

- i. PCI of non-target vessels 24 hours to 30 days prior to enrollment if successful and uncomplicated as defined above.
- ii. In addition, in cases where non-target lesion PCI has occurred 24-72 hours prior to the baseline procedure, at least 2 sets of cardiac biomarkers must be drawn at least 6 and 12 hours after the non-target vessel PCI.
- iii. If cardiac biomarkers are initially elevated above the local laboratory upper limit of normal, serial measurements must demonstrate that the biomarkers are falling.

d. Over 30 days prior to Baseline Procedure:

PCI of non-target vessels performed greater than 30 days prior to procedure whether or not successful and uncomplicated.

5. Patient or legal guardian is willing and able to provide informed written consent and comply with follow-up visits and testing schedule.

Angiographic inclusion criteria (visual estimate)

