7.6 Procedures That Take into Account All the Data

The analysis of the primary endpoint will be performed using the following datasets, as appropriate:

- **Full Analysis Set (FAS):** All subjects who have been enrolled into the trial, regardless of whether they received the study stent or not. Subjects are included in the FAS once the stent has been advanced beyond the guide catheter. If the study stent is not advanced beyond the guiding catheter, the patient will be de-registered and will not be considered part of the full analysis set.
- **Per-Protocol (PP) Analysis Set:** All subjects in the Full Analysis Set (FAS) with no major protocol deviations will be included in the Per-Protocol Analysis Set. Major protocol deviations include, but are not limited to, enrollment of a subject:
 - ✓ whose informed consent was not properly obtained
 - ✓ who did not meet all of the inclusion or exclusion criteria
 - ✓ who did not receive at least 6 months of DAPT post baseline procedure
- **Safety Analysis Set:** The safety analysis set will include all subjects, including de-registered subjects, who signed an informed consent and who had any trial-related activities.

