All deaths are considered cardiac unless an unequivocal non-cardiac cause can be established. Specifically, any unexpected death even in patients with coexisting potentially fatal non-cardiac disease (e.g. cancer, infection) should be classified as cardiac.

Cardiac death:

Any death due to proximate cardiac cause (e.g. MI, low-output failure, fatal arrhythmia), unwitnessed death and death of unknown cause, all procedure related deaths including those related to concomitant treatment.

Vascular death:

Death due to non-coronary vascular causes such as cerebrovascular disease, pulmonary embolism, ruptured aortic aneurysm, dissecting aneurysm, or other vascular cause.

Non-cardiovascular death:

Any death not covered by the above definitions such as death caused by infection, malignancy, sepsis, pulmonary causes, accident, suicide or trauma.

DEVICE DEFICIENCY

See Section 14 for definition of device deficiency.

DIABETES MELLITUS (DM)

History of diabetes mellitus. The condition will be further categorized as treated by diet, oral hypoglycemic medications, or insulin.

DISSECTION

NHLBI Dissection Classification System:

- Grade A: Minor radiolucencies within the lumen during contrast injection with no persistence after dye clearance.
- Grade B: Parallel tracts or double lumen separated by a radiolucent area during contrast injection with no persistence after dye clearance.
- Grade C: Extraluminal cap with persistence of contrast after dye clearance from the lumen.
- Grade D: Spiral luminal filling defects.
- Grade E: New persistent filling defects.
- Grade F: Non-A-E types that lead to impaired flow or total occlusion.

Note: Grade E and F dissections may represent thrombus.

DISTAL EMBOLIZATION

Distal embolization is defined as new abrupt cut off or filling defect distal to the treated lesion.

IN-STENT PERCENT NEOINTIMAL HYPERPLASIA

In-stent percent neointimal hyperplasia will be calculated as neointimal hyperplasia (NIH) divided by stent volume. Volumetric analysis will include measurement every 1mm of the stent and lumen cross-sectional areas (CSA). NIH will be calculated as stent minus lumen. Once a complete set of CSA measurements will be obtained, stent and NIH volumes will be calculated using Simpson's rule. Volumetric analysis will be performed only for lesions in which motorized pullback was consistent and reliable.

IN-STENT RESTENOSIS - MEHRAN CLASSIFICATION (13)

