3.0 ANALYSIS SETS

Full Analysis Set (FAS): All subjects who have been enrolled into the trial, regardless of whether they received the study stent or not will be included in the FAS. Subjects are included in the FAS once the EluNIR 38 mm stent has been advanced beyond the guide catheter. If the study stent is not advanced beyond the guiding catheter, the patient will not be enrolled in the trial.

Per-Protocol (PP) Population: All subjects in the Full Analysis Set (FAS) with no major protocol deviations as identified by the Medical Monitor will be included in the Per-Protocol Analysis Set. Major protocol deviations may include the following categories:

- Informed consent was not properly obtained
- Inclusion or exclusion criteria deviations
- Not receiving DAPT post-baseline procedure according to the standard of care

Major protocol deviations will be identified by the Medical Monitor prior to the database lock for the primary analysis.

Safety Analysis Set: All subjects, including subjects who are consented but do not meet eligibility criteria and not in the FAS will be included in the Safety Analysis Set. Safety Analysis Set will also include all FAS patients.

Table 2 summarizes the analysis sets to be used for each type of analyses.

 Cardiovascular Research Foundation	FORM		Document N° BIO-TMP-0702 Revision: 00
	TITLE SAP Template		Effective date: 16-Mar-2018 Department: BIO

Table 2 Analyses and analysis sets

Endpoint	FAS	PP Analysis Set	Safety Analysis Set
Primary endpoint	X	X	
Secondary endpoints	X	X	
AEs, Other Safety Data			X
Demographics/baseline characteristics	X		
Angiographic Core Lab Analysis	X		

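### Consent is signed after PCI and every analysis set depends on it, so an otherwise eligible patient who dies before anyone signs is in no analysis set, and that loss can only raise the reported success rate.

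*Protocol*

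**What the plan says.** Protocol 6.3.4 gives the conditions for enrollment: all eligibility criteria met, a 38 mm stent passed beyond the guiding catheter, and then "the patient has signed an informed consent (post-procedure), the patient will be enrolled into the trial". SAP 1.2 repeats this.

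The analysis sets follow from it:

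- **FAS.** SAP 3.0 defines it as "All subjects who have been enrolled into the trial". Protocol 6.1.6 says that patients without consent "will not count towards the sample size of approximately 50 subjects and will not be included in the FAS".
- **Per-protocol set.** It is a subset of the FAS (Protocol 7.6, SAP 3.0).
- **Safety Analysis Set.** Protocol 7.6 limits it to subjects "who signed an informed consent and who had any trial-related activities". SAP 3.0 describes it as the FAS plus patients who consented but were ineligible.

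On data, footnote 1 of Table 1 in Protocol 6.1.4 says "Data will be collected only after post-procedural informed consent has been obtained", and 6.1.4.4 rules out collecting data on patients who do not consent.

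Protocol 6.3.4 names selection bias and sets two controls. All eligible patients are to be approached whatever the procedural result. Sites also keep a log of every 38 mm stent passed beyond the guiding catheter, in which they "document eligibility and patient consent versus refusal to participate in the study". SAP 5.1.1 tabulates numbers screened, enrolled and discontinued, with reasons for discontinuation.

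**The concern.** The primary endpoint is device success with no MACE within 30 days (Protocol 6.1.3.1), and MACE includes cardiac death. The risk begins when the stent enters the artery, and the plan means to capture events from that point: Table 1 footnote 7 records adverse events from then on. Membership of every analysis set begins later, at the signature. A death between the two leaves both numerator and denominator.

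The trial has a single arm, so no control group shares the loss and offsets it. The lost patients would be failures by default, so the direction is fixed. The death would also be outside the adverse event tables, which use the Safety Analysis Set (SAP Table 2), although Protocol 7.1 justifies the sample size by the chance of seeing at least one device-related adverse event.

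**Working it through.** **1. The plan's own figure.** Protocol 7.1 uses P(at least one event) = 1 − (1 − p)^n. With n = 50 and p = 0.032 this is 1 − 0.968^50 = 0.803. The stated 80% reproduces. It applies to the patients who are observed, that is, those who consented.

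**2. Tracing the patient through the rules.** Take a patient who meets all criteria other than inclusion criterion 5 ("Patient or legal guardian is willing and able to provide informed written consent"), in whom the 38 mm stent passes the guiding catheter, and who dies before anyone signs.

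- Eligibility otherwise refers to the condition before PCI (note in Protocol 6.3.1), so the fatal complication does not itself exclude the patient.
- No signature means not enrolled, so not in the FAS and not in the per-protocol set.
- No signature also means not in the Safety Analysis Set.
- The sentence in Protocol 7.6 and SAP 3.0 that includes subjects once the stent is past the guide catheter does not rescue the patient. It qualifies a set of enrolled subjects, and 6.1.6 excludes those without consent.
- Protocol 19.1 states "All deaths are considered cardiac unless an unequivocal non-cardiac cause can be established", and it counts all procedure-related deaths as cardiac. The default outcome is therefore MACE and endpoint failure.
- The best-case and worst-case table in SAP 5.2.2 imputes for subjects with missing primary-endpoint data. This patient is not a subject.
- Vital status from public records (Protocol 6.3.3.3) is foreseen only for subjects who withdraw.

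**3. Direction.** Let s be the successes among 50 consented subjects and k the omitted deaths counted as failures. Patients without consent do not count towards the 50, so the denominator with them is 50 + k. The reported rate is s/50 and the rate with them is s/(50 + k), which is lower for any s > 0 and k > 0.

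**4. Size per death.** The documents give neither s nor k, so these are illustrations. Intervals are exact (Clopper-Pearson) 95%: lower limit Beta(0.025; x, n − x + 1), upper limit Beta(0.975; x + 1, n − x).

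| Reported | With one omitted death | Shift |
|---|---|---|
| 50/50 = 100.0% (92.9 to 100.0) | 50/51 = 98.0% (89.6 to 100.0, rounded) | 2.0 points |
| 48/50 = 96.0% (86.3 to 99.5) | 48/51 = 94.1% (83.8 to 98.8) | 1.9 points |
| 45/50 = 90.0% (78.2 to 96.7) | 45/51 = 88.2% (76.1 to 95.6) | 1.8 points |

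Each shifted estimate lies inside the interval that would be reported.

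**5. How likely.** The documents give no risk r of death before consent. For assumed values, the chance of at least one in 50 attempts is 1 − (1 − r)^50, and the expected shift is r times the success rate, here 96%.

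| Assumed r | Chance of at least one | Expected shift |
|---|---|---|
| 0.1% | 4.9% | 0.10 points |
| 0.2% | 9.5% | 0.19 points |
| 0.5% | 22.2% | 0.48 points |
| 1% | 39.5% | 0.96 points |

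Nothing in the documents supports the upper end of this range.

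**The case against.** The sponsor can answer that this is a reasoned and disclosed choice. Protocol 6.3.4 explains consent after PCI (PCI of long lesions is uncommon, and the stent is already marketed in Israel), names selection bias and sets controls. The log is keyed to stents, not survivors, so a patient who dies should be on it. All of this stands. What the visible wording lacks is a category that separates such a death from a refusal or from ineligibility under criterion 5.

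The group is also narrow. Shock, intubation, LVEF below 30% and STEMI within 24 hours are exclusions. A legal guardian or authorized representative may sign (Protocol 6.3.1 and section 12), which may capture some incapacitated patients while they live. That reduces the gap but does not close it, because nothing provides for consent after death.

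It can be said that such a patient is ineligible by criterion 5, so the endpoint never applied. Formally this is right, and it is the mechanism itself: inability to sign is here a consequence of the outcome.

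The trial is descriptive, with no test and no performance goal, so no planned decision turns on 1.9 points. This stands and limits the weight of the point.

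Two stronger readings are tempting, and the documents do not support them:

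- A reader might infer that zero deaths and unreported deaths could never be told apart. If the screened count in SAP 5.1.1 comes from the log and equals the enrolled count, no logged patient was lost. The ambiguity arises only when the counts differ.
- A reader might infer that the plan has no category at all for these deaths. Figure 1 and the log form are not shown, and either could hold one.

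**Conclusion.** The structural point holds. Under the stated set rules, an otherwise eligible patient who dies between stent passage and signature is in no analysis set, and the default classification makes that death a primary-endpoint failure. For deaths so classified, the bias in the success rate can only be upward. A death with an unequivocal non-cardiac cause would be an exception.

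The size is about 1.8 to 2.0 points per death at 45 to 50 successes in 50. The number of such deaths cannot be derived from the documents, is probably small and may be zero. It would be wrong to conclude that the primary estimate is known to be biased, or that counting these deaths as failures gives a corrected estimate. Anonymous deaths cannot be adjudicated, and patients who refuse after a poor result stay outside the FAS.

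The conclusion rests on the visible log wording and SAP 5.1.1. If Figure 1 or the log form already records death before consent, only the reporting step remains. This is a cheap improvement that should be made; it is not a flaw that invalidates the design.

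**What to change.** 1. In the existing screening log, record one anonymous reason for non-enrollment for each patient with an advanced 38 mm stent who met all criteria other than inclusion criterion 5: refused, died before consent, or other.
2. Report these counts, including zero, in the disposition table of SAP 5.1.1. Report them for the whole trial and not by site, because sites are small (at least 5 subjects anticipated, at most 20, Protocol 7.8).
3. Only if the count of deaths before consent is above zero, add one row to the sensitivity table of SAP 5.2.2 with these deaths added to the FAS as failures and an exact 95% interval. Label it an unadjudicated worst-case bound, and state that it does not correct for refusals.

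The FAS and the primary analysis stay as they are. The cost is one field in a log that sites already keep, a few counts in a planned table and possibly one extra row. The ethics committee must confirm that anonymous trial-level counts are compatible with Table 1 footnote 1 and with Protocol 6.1.4.4. The bound, if needed, may be slightly less favourable than the primary result.

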6.3.5 Total Expected Duration of the Clinical Investigation

The clinical investigation will last from Q3 2018 until approximately Q4 2019.

6.3.6 Expected Duration of Each Subject's Participation

Each subject will remain in the clinical investigation for approximately 1 year from the time of the study stent implantation until the last follow-up telephone contact.

The subjects will not be provided any follow-up contact or medical care related to the trial after the clinical investigation has been completed.

6.3.7 Number of Subjects Required to Be Included in the Clinical Investigation

Approximately 50 subjects will be enrolled in this study. This sample size (n=50) provides 80% power to observe at least one device-related AE if occurring with an incidence of 3.2%. (see statistical considerations section for additional details).

6.3.8 Estimated Time Needed to Complete Study Enrollment

The enrollment period is expected to last one year.

6.4 Procedures

6.4.1 Baseline Angiography

Baseline angiography of the target vessel will be completed as per the Angiographic Core Laboratory Protocol contained in the Study Binder. Angiography of non-target vessels (if required) may be performed per site standard.

Assessment of angiographic eligibility is based on a visual assessment of the immediate pre-procedure angiogram obtained by the Investigator. Use of a 6 French or larger guide catheter is recommended for accurate QCA measurements. Following intra-coronary injection of nitroglycerin (50-200 mcg IC nitroglycerin or per standard hospital practice), baseline angiography of the involved vessel will be performed for at least two orthogonal views showing the target lesion free of foreshortening or vessel overlap according to the Angiographic Core Laboratory Guidelines. Angiographic images of the target lesion must be sent to the Angiographic Core Laboratory per specified shipping method.

6.4.2 Non-Target Vessel PCI and Non-Target Lesion PCI in Target Vessel

- All non-target vessel PCI must be treated prior to the screening for eligibility.
- Non-target lesion PCI in the target vessel is allowed but must have occurred ≥ 12 months prior to the baseline procedure.

The following are the criteria for non-target vessel PCI (as summarized in [Table 3](#)):

During Baseline Procedure: The non-target vessel PCI must be successful and uncomplicated before screening of the subject for eligibility. Successful and uncomplicated is defined as <50% visually estimated residual diameter stenosis, TIMI Grade 3 flow, no dissection \geq NHLBI type C,

no perforation, no persistent ST segment changes, no prolonged chest pain, no TIMI major or BARC type 3 bleeding.

Within 24 hours prior to Baseline Procedure: PCI of non-target vessels are NOT allowed within the 24 hours immediately preceding the baseline procedure and enrollment.

24 hours to 72 hours prior to Baseline Procedure: Non-target lesion PCI can be performed 24 to 72 hours prior to the baseline procedure. In this case, at least 2 sets of cardiac biomarkers must have been drawn at least 6 and 12 hours after the non-target vessel PCI, according to the local standards. If the biomarkers are initially elevated above the local laboratory upper limit of normal, the serial measurements must demonstrate that the biomarkers are falling.

72 hours to 30 days prior to Baseline Procedure: PCI of non-target vessels can be performed 72 hours to 30 days prior to baseline procedure if PCI was successful and uncomplicated.

More than 30 days prior to Baseline Procedure: PCI of non-target vessels may be performed more than 30 days prior to baseline procedure whether successful and uncomplicated or not.

Table 3: Summary of Timing of Non-Target Vessel According to PCI Rules

Non-Target Vessel PCI Decision Matrix	During Baseline Procedure	Time prior to Baseline Procedure			
		<24 hours	24 hours to 72 hours	72 hours to 30 days	>30 days
Is PCI of a non-target vessel allowed?	Yes	No	Yes	Yes	Yes
Is procedural success required?	Yes	N/A	Yes	Yes	No
Must the procedure be uncomplicated?	Yes	N/A	Yes	Yes	No
Are serial biomarkers required?	No	N/A	Biomarkers must be negative post procedure or falling (at least 2 sets of measurements)	No	No

N/A = not applicable

